#### 3 OBJECTIVES AND ENDPOINTS

The aim of this trial is to demonstrate if discontinuation of nocturnal use of absorbent pants in children with NE has any impact on the rate of spontaneous resolution of NE, compared with continued use of absorbent pants, over a period of 4 weeks. It is hypothesised that children discontinuing or continuing the use of absorbent pants will show statistically equivalent outcomes (number of dry nights) at the end of a 4-week trial period.

A secondary aim of this trial is to demonstrate that the continued use of absorbent pants has a positive impact on QoL outcomes and sleep quality for both parents and children, compared with discontinuation of absorbent pants.

Study objectives and endpoints are listed in Table 1.

<sup>1 Certification mark that indicates conformity of the product with the requirements of the applicable European Community directives.

**Table 1 Study Objectives and Endpoints** 

Objectives	Endpoints
Primary	
To determine if discontinuing the use of DryNites® absorbent pants over a period of 4 weeks has any impact on the rate of spontaneous resolution of NE compared with continuing use of DryNites® absorbent pants	Average number of wet nights in Week 8 (last week of the intervention period)
Secondary	
To determine if using DryNites® absorbent pants improves the child's Quality of Life (QoL) assessed by the Paediatric Incontinence Questionnaire (PinQ) compared with not using absorbent pants	• Change from baseline in total PinQ score at Day 56 ± 7days
To determine if using DryNites® absorbent pants improves the parent/carer's QoL assessed by the World Health Organization Quality of Life BREF (WHOQoL-BREF) compared with not using absorbent pants	• Change from baseline in total score of each domain at Day $56 \pm 7$ days
To determine if using DryNites® absorbent pants improves the child's sleep assessed by the Paediatric Daytime Sleepiness Scale (PDSS) compared with not using absorbent pants	• Change from baseline in total PDSS score at Day 56 ±7 days
To determine if using DryNites® absorbent pants improves the parent/carer's sleep assessed by the Checklist Individual Strength questionnaire (CIS) compared with not using absorbent pants	Change from baseline in subscale scores at Day 56     ±7 days
To determine if DryNites® absorbent pants offer different benefits or limitations to previously used absorbent pants/nappies	Descriptive statistics

# 4 METHODOLOGY

# 4.1. Study Design

This is an 8-week randomised, open-label, 2-arm, parallel-group Phase IV trial with a 2:1 allocation ratio for discontinuation of continuation of use of DryNites® absorbent pants in children with NE, with an optional 4-week extension period. This will be an equivalence trial for the primary endpoint.

Eligible patients are children with monosymptomatic NE, not previously treated for NE, and managed with absorbent pants/nappies (any brand) for a minimum of 6 months. Participants must be dry at day for at least 6 months. Participants will be divided in 2 age groups of similar

size. The younger age group will be comprised of participants aged 4-<6 years old and the older age group will be comprised of participants aged  $\ge 6-8$  years old. Capping of the faster recruiting subgroup will be implemented if needed.

Participation in the study will be proposed for all children meeting the above conditions; parents/carers should be given sufficient time to review the study information and provide informed consent to their child's and their participation. Children's assent will be requested for the older age group.

The study consists of 3 consecutive periods of 4 weeks each, including the run-in, the intervention (core trial) period, and the extension period.

Participant meeting the eligibility criteria will enter the run-in period. During the 4-week run-in period, all participants will be assigned to using DryNites® every night.

Participant meets the inclusion criterion of NE 7 nights per week during the last week of the run-in period will be randomised to participate in the intervention (core trial) period. During the 4-week intervention period, participants will be assigned to either stopping the use of absorbent pants or continuing DryNites® in a 2:1 ratio. All participants will receive absorbent bed mats to use every night, however, the use of bed mats is optional.

Following completion of the 4-week intervention period, participants will be invited to participate in the optional 4-week extension. During the optional 4-week extension period, participants will remain on their randomly assigned treatment for an additional 4 weeks.

Study specific mandated clinic visits will be required as part of the participation in this study. Baseline, randomisation, and any subsequent visit (i.e., Visit 3 and 4) can also be performed remotely in case the patient cannot visit the site in person. Participants will be assessed on Day 0 (baseline), Day  $28 \pm 7$ days (end of run-in and randomisation), Day  $56 \pm 7$ days (end of intervention/core trial period), and Day  $84 \pm 7$ days (end of extension period).

Participants will be reimbursed for their travel expenses, where applicable.

[figure not shown]
Dry and wet nights will be captured every day from the start of the run-in period to discontinuation of the study through an electronic diary, accessible through the parent's/carer's own device (smart phone, tablet, or computer).

Quality of life (QoL) and sleep questionnaires will be completed by children and parents/carers in electronic format on-site during the clinic visit, using site-based hand-held devices (e.g., tablets) or computers, from randomisation onwards. In case the questionnaires are not completed during the clinic visit or if a visit is performed remotely, the questionnaires will be accessible through the parent's/carer's own device. Questionnaires will be accessible after the visit and should be completed as close to the visit as possible (and before the next visit).

The perception of the absorbent products will be assessed by 2 questionnaires, at study entry (on previous absorbent products) and at the end of the run-in period (on DryNites®, compared to the previously used absorbent pants/nappies).

An overview of the trial design is provided in Figure 1.

Figure 1 Study Design

# 4.2. End of Study Definition

A patient is considered to have completed the study if he/she has completed all phases of the study including the last visit of the core trial period or the last scheduled procedure of the extension period.

The end of the study is defined as the date of last scheduled procedure for the last patient included in the optional extension period of the study globally.

# 4.3. Study Population

The study will aim to randomise approximately 120 participants aged 4-8 years from a total of 7-12 sites in 3 countries (Belgium, Denmark, and the United Kingdom) over a 30-month enrolment period. Children/parents/carers actively seeking help for NE can be recruited via specialist centres, clinician visits, referrals, and collaboration with primary care providers (PCPs).

Sites that are routinely involved in the care and treatment of patients with NE will be targeted for recruitment. Selection criteria and basic site information (e.g., site size, Investigator specialty, site type) will be collected via a site qualification survey.

All children/parents/carers actively seeking help and those who had not previously considered medical assistance, will be considered for study participation, and assessed for eligibility according to the defined selection criteria. A screening log will be maintained by each site to record the disposition of consecutive patients, potentially eligible for study participation.

The following options will be considered to reach the target enrolment:

- Advertising through notices in hospitals and PCP clinics may attract participants to the study
- Newspaper advertising could also be used.

#### 4.3.1. Inclusion Criteria

The following criteria must be met for the participant to be enrolled in the study:

- 1. Patient aged between 4–8 years at the time of enrolment
  - a. To be categorised in the younger participant group, participants must be aged 4-<6 years
  - b. To be categorised in the older participant group, participants must be aged ≥6-8 years
- 2. Have a clinical diagnosis of monosymptomatic primary NE
- 3. Have been dry in the day for  $\geq 6$  months prior to enrolment
- 4. Have on average no more than 1 dry night per month during the past 6 months at enrolment
- 5. Using absorbent pants/nappies to manage NE for at least 6 months prior to enrolment
- 6. Have an informed consent form (ICF) signed by their parent(s)/carer(s)
- 7. For randomisation: have NE 7 nights per week over Week 4/last week of the run-in period

#### 4.3.2. Exclusion Criteria

Patients meeting ANY of the following criteria are not eligible for participation:

1. Children in foster/court care

- 2. Have implemented any previous intervention to address NE (use of prescribed alarm schedule, desmopressin, imipramine, anticholinergics), or withdrawal of pants/nappies for >7 days in the previous 6 months
- 3. Have secondary NE
- 4. Have wetting in the day
- 5. Have faecal soiling
- 6. Have known urinary tract disease
- 7. Have diabetes
- 8. Receive any regular intake of medication
- 9. Have a known developmental/neurological disorder
- 10. Have links to Kimberly-Clark of any kind (including family relations employed by Kimberly-Clark, holding stocks or shares in Kimberly-Clark)

# 4.3.3. Patients Screening and Registration

The Investigator will:

- 1. Obtain signed informed consent from the parent(s)/carer(s) of the potential patient (and paediatric assent if applicable) before any study specific procedures are performed that are not part of routine medical care
- 2. Generate the patient's identification from the electronic data capture (EDC)
- 3. Determine patient's eligibility
- 4. Obtain a unique patient randomisation number through the Interactive Web Response System (IWRS). This number is part of the patient's identifier and will be maintained throughout the study

If a patient does not meet eligibility criteria or withdraws from participation in the study, then their number cannot be reused.

#### 4.3.4. Screen Failures

Screen failures are defined as patients who were consented to participate in the study but are not subsequently randomly assigned to study treatment, for any reason identified before, during, or at the end of the run-in period.

A minimal set of screen failure information is required to ensure transparent reporting of screen failure subjects to meet the Consolidated Standards of Reporting Trials (CONSORT) publishing requirements and to respond to queries from regulatory authorities. Minimal information

includes demographics, screen failure details, eligibility criteria, and any serious adverse event (SAE).

These patients should have the reason for study withdrawal recorded as 'Screen failure'; this reason for study withdrawal is only valid for patients who were not randomised.

Individuals who do not meet the criteria for randomisation in this study may be re-screened one time, after an additional run-in of 1 week.

# 4.3.5. Methods for Assigning Patients to Treatment Groups

A patient randomisation list will be produced using permuted block randomisation stratified by age group (4–<6 years old and  $\ge6-8$  years old) and a 2:1 group allocation for discontinuation or continuation of the use of DryNites® pyjama pants.

When a patient is qualified for entry into the randomised treatment period, treatment assignment will be performed by means of an IWRS on a central level on Visit 2 (Day  $28 \pm 7$  days).

Before the study is initiated, the log in information and directions for the IWRS will be provided to each study centre.

The Investigator or his/her delegate (study coordinator) will log on to the EDC and confirm that the patient fulfils the eligibility criteria and proceed with the randomisation. Participants will be assigned a unique number (randomisation number) in ascending numerical order on the next available record in the group at each study centre. The randomisation number encodes the participant's assignment to 1 of the 2 arms of the study (No Pants arm or DryNites® arm).

The treatment assignment (Discontinuation vs. continuation of DryNites®) will be captured in the EDC from the IWRS.

#### 4.3.6. Patient Withdrawal and Discontinuation of Study Treatment

Any individual participant will be withdrawn from the study if any of the following criteria apply:

- Withdrawal of parents/carers consent, for any reason
- Investigator's decision
- Adverse event (AE)
- Initiation of a prescribed therapy for NE (pharmacologic or bed alarm)

- Severe non-compliance with the study clinical investigation plan, including deviations to eligibility criteria and non-compliance with the study procedures
- Participant's death
- Participant lost to follow-up

Parents/carers may withdraw consent and discontinue the patient's participation in the study at any time, for any reason with no effect on their medical care or access to treatment. If consent is withdrawn prior to completing the study core and/or extension period, the parents/carers will always be asked about the reason(s) and the presence of any AEs. Any known reason for withdrawal should be documented in the electronic case report form (eCRF). The Investigator will follow-up AEs outside of the clinical study.

If a participant is withdrawn from participation in the study, then his/her enrolment code cannot be reused. Withdrawn participants will not be replaced.

All information already collected as part of the study will be retained for analysis; however, no further efforts will be made to obtain or record additional information regarding the participant. The Investigator may discontinue a participant from the study treatment at any time if the Investigator considers it necessary, due to medical reasons, ineligibility (either arising during the study or retrospectively having been overlooked at screening), significant deviation from the clinical investigation plan, significant non-compliance with study requirements.

The Investigator should document any deviation from the clinical investigation plan regardless of their reasons.

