#### 4.7.2. Direct-to-Patient Data Collection

The following data will be collected daily for all enrolled patients using an electronic diary from the morning following the baseline visit until discontinuation from the study:

- Were absorbent pants worn? Yes/No/Another brand
- Was the bed mat used? Yes/No/Another brand
- Did the child have an NE event? Yes/No
- How was the NE event managed? One response to be selected: Child slept through the night; child awoke but did not take any action; child awoke and changed pants/changed bed/visited toilet but did not disturb parents; child awoke and woke parents.

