## 4.7.6. Disposition/End of Study

The following data will be collected for all enrolled patients at the time of discontinuation:

- AEs occurred since the previous visit. All AEs ongoing at the time of discontinuation will be followed up until resolution or stabilisation of for 30 days, whichever occurs first
- Concomitant medication for AEs
- Review of diary data
- PROs: PinQ, WHOQOL, PDSS, CIS (for participants who were randomised)
- Date of completion/discontinuation
- Primary reason for discontinuation

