Analyses of these 4 questionnaires will be provided by group on the Randomised Set. Frequency distribution and descriptive statistics, when applicable, will be provided by visit for each item of questionnaires, while summary statistics for total scores, domain scores and changes from baseline will be provided as applicable for the PinQ, WHOQoL-BREF, PDSS and CIS.

The effect size will be also presented as descriptive statistics of ratio between the change from baseline and baseline SD.

The percentage of patients with change from baseline  $\geq 0.5$  time the SD will be also provided. For applicable questionnaires, a covariance analysis model (ANCOVA) with baseline PROs value as covariate will be performed. Group comparisons will be performed for the difference in least squares means (LSMean) at Day  $56 \pm 7$  days. LSMean (standard error [SE]) by group and visit (if applicable), the LSMean difference between groups, along with 95% confidence limits of the group differences and the p-value for the group comparison will be displayed. For the change from baseline, p-value for the within-group difference will also be displayed.

The same analysis will be repeated using a repeated measure model to assess the extension period effects.

The Absorbent Pants Clinical Trial Questionnaire administered at study entry, and the DryNites® Clinical Trial Questionnaire administered at the end of the run-in period, will be analysed descriptively for the Screened Set.

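### Scheduled follow-up ends when a child is withdrawn for starting NE therapy or for severe non-compliance, so Week 4 diary counts and Day 56 questionnaires are missing or mistimed for some randomised children

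*Protocol*

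**What the plan says.** Protocol 4.3.6 opens its list with "Any individual participant will be withdrawn from the study if any of the following criteria apply". Besides withdrawal of parental consent, the list includes starting a prescribed therapy for NE (drug or alarm) and "Severe non-compliance with the study clinical investigation plan, including deviations to eligibility criteria and non-compliance with the study procedures". Data already collected are kept, but "no further efforts will be made to obtain or record additional information regarding the participant".

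Protocol 4.7.2 has the daily diary run "from the morning following the baseline visit until discontinuation from the study".

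Protocol 4.7.6 begins "The following data will be collected for all enrolled patients at the time of discontinuation". It then lists adverse events, diary review and, for randomised children, all four questionnaires. The end-of-study column of Protocol Table 2 agrees.

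On analysis, Protocol 5.4.2 says "Analyses of these 4 questionnaires will be provided by group on the Randomised Set", and SAP 15.2 says the same. The default is to analyse whoever has a value (Protocol 5.4.5, SAP 8.3). SAP 7.3, Table A, assigns study days 2 to 42 after randomisation to Visit 3, and the ANCOVA in SAP 15.2.3 compares the arms at Visit 3.

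**The concern.** Two of the listed reasons for leaving the study are departures from the assigned regimen or procedures, not refusals to give data. Parents in either position may be quite willing to go on recording, but the protocol does not ask them to.

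These departures are unlikely to be random. A family that seeks treatment, or does not keep to its assigned arm, may do so because of wet beds or poor sleep. The trial is open-label and the two arms carry different burdens, so the rate and the reasons may differ by arm. This is a reasoned expectation; the documents give no rates.

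At stake are the questionnaire comparisons on the Randomised Set, the descriptive diary summaries on that set (Protocol 5.4.2, SAP 15), and the possibility of checking the equivalence conclusion in all randomised children. Data not collected cannot be restored at analysis.

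**Working it through.** **1. What is collected for a child withdrawn before Week 4.**
- Diary: ends at discontinuation (4.7.2), so there is no true Week 4 count.
- Questionnaires: one set at discontinuation (4.7.6), none at Day 56.
- Sections 4.3.6 and 4.7.6 can be read together as one last assessment and then nothing, but neither says so. As worded they conflict.

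**2. Where the early questionnaire goes.** Take randomisation on Day 28 as study day 1. Day 56 is then study day 29, and the protocol's ±7 days is study days 22 to 36, a span of 15 days. The SAP window of days 2 to 42 spans 41 days. A discontinuation questionnaire on study days 2 to 21 is outside the protocol window, by date up to 29 − 2 = 27 days before Day 56, yet is labelled Visit 3. SAP 7.3 also uses visit dates with these windows to cut the diary, so the same substitution is possible there.

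**3. Questionnaires.** Error in an arm mean = f × d, where f is the share withdrawn and d is the difference between withdrawn and retained children at Day 56. Assumptions, not document figures: f = 10–20% of the no-pants arm, none in the other arm, d = 0.5–1.0 SD.
- Low end: 0.10 × 0.5 = 0.05 SD.
- High end: 0.20 × 1.0 = 0.20 SD.

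The sign of d is unknown, so the error could go either way. If an early questionnaire is used instead, d becomes the gap between that value and the unseen Day 56 value.

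**4. Wet nights, all randomised.** First, the plan's own figures. Expected weekly means are 7 × 0.95 = 6.65 (continuing) and 7 × 0.80 = 5.60 (discontinuing), a difference of 1.05 against a margin of 2 nights in 7. For power at 15 and 30 children, SE = √(0.95×0.05/105 + 0.80×0.20/210) = 0.0348, and Φ((2/7 − 0.15)/0.0348 − 1.96) = 97.3%. Simulation of the risk-difference interval gives 97.7%, against the stated 99%.

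Now let a share f of the no-pants arm be unseen, with w wet nights each, and let the observed means equal the plan's. The all-randomised difference is 6.65 − [(1 − f) × 5.60 + f × w], with w from 7 to 0:

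| f | w = 7 | w = 0 |
|---|---|---|
| 10% | 0.91 | 1.61 |
| 20% | 0.77 | 2.17 |
| 25% | 0.70 | 2.45 |

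With w = 0 the point estimate reaches 2 nights when 5.60 × (1 − f) = 4.65, that is f = 17%. These are outer bounds, not forecasts.

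**5. Does imputation cover this?** SAP 15.1.2 starts multiple imputation for the primary endpoint at 20% missing and assumes missing at random. The denominator is not stated. If it is all randomised children, with 80 and 40 of 120, losing 20% of the no-pants arm is 16/120 = 13.3%. The trigger needs 24/80 = 30% in that arm, with none lost in the other. For the questionnaires, SAP 15.2.2 deals with missing items, not missing visits.

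**6. Loss of numbers is the lesser issue.** With the pooled t interval and all 120 randomised, simulated power is still 99.9% after 25% loss. Within one age group of 60 it falls from 97.5% to 91.2%.

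**The case against.** Several stronger readings are tempting, and the documents do not support them.

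- *All data collection stops.* It does not. Section 4.7.6 and Table 2 require a final set of questionnaires and a diary review, and ongoing adverse events are followed to resolution, stabilisation or 30 days.
- *Day 56 questionnaires are simply absent.* Under Table A an early value can take their place. The fault is as much timing as absence.
- *Leaving the regimen means leaving the study.* Only severe non-compliance triggers withdrawal. Other pants-use departures are counted from the diary over the four weeks and handled by exclusion at analysis (Protocol 4.3.8), so those children go on recording.
- *The primary result is biased by this rule.* The Primary Analysis Set already excludes NE-therapy starters and children over the pants-use limit (Protocol 4.3.8, SAP 6.4). More diary data from them would leave the planned result largely as it is. The exception is a child withdrawn for severe non-compliance of another kind.
- *The no-pants arm will look too good.* The sign is not established. The trial's own hypothesis is that pants improve quality of life and sleep, so a family that returned to pants might score better at Day 56.
- *No method could recover the data.* Multiple imputation is specified for the primary endpoint and a repeated-measures model for the extension analysis. Both rest on missing at random, which is doubtful here, but the stronger statement is not shown.

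It is also fair to say that SAP 15.2.3 calls the questionnaire p-values purely exploratory and SAP 8.1 plans no confirmatory testing. That limits the weight of the point. It does not remove it, because these comparisons are the stated secondary objectives.

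**Conclusion.** The point holds in a limited form. For children withdrawn before the end of the intervention period without withdrawal of consent, true Week 4 counts and Day 56 questionnaires are not collected, and an early questionnaire may be analysed as if it were the Day 56 one. The reasons for withdrawal are plausibly linked to outcome and arm.

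The effect falls on the Randomised Set questionnaire comparisons and diary summaries, and on any all-randomised sensitivity analysis of the primary endpoint, of which none is planned outside the imputation rule. It falls little on the planned primary result.

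Size and direction cannot be stated from the documents. The 0.05–0.20 SD and the wet-night bounds rest on assumed withdrawal shares and assumed unseen outcomes, with all withdrawals in one arm. The change is worth making because it is cheap and the data cannot be obtained later.

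**What to change.** **Protocol 4.3.6:** separate stopping the assigned regimen from withdrawing consent. Unless consent is withdrawn, continue the e-diary through Week 4 and collect the Day 56 questionnaires remotely, with a flag on data recorded after the regimen changed. This concerns data collection only and leaves the clinical grounds for stopping a regimen untouched.

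**Protocol 4.3.6 and 4.7.6:** reconcile the two sections, so that it is clear what is collected at discontinuation and what afterwards.

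**SAP 7.3 and 15.2.3:** for Visit 3, use the questionnaire closest to Day 56. Do not treat an early-discontinuation questionnaire as the Day 56 value; summarise it separately.

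**Cost:** changes to protocol, consent and SAP wording, and for the families concerned at most about four to five more weeks of short diary entries and one set of questionnaires. If 10–20% of about 80 no-pants children were withdrawn, that would be 8 to 16 families. The diary and questionnaires already run on the parents' own devices.
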